## 3 STATISTICAL ANALYSES

### 3.1 GENERAL CONSIDERATIONS

In general, continuous data will be summarized using the number of observations available, mean, standard deviation (SD), median, (Q1 and Q3 as needed), minimum, and maximum. Categorical and ordinal data will be summarized using the count and percentage of participants.

The baseline value is defined as the last available value before the first dose of double-blind investigational medicinal product (IMP). For participants randomized but not treated, the baseline value is defined as the last available value before randomization.

The baseline value of platelet count is defined as the average of a patient's three platelet counts before the first dose of double-blind IMP: the two qualifying platelet counts at screening collected in eCRF and the platelet count at Week 1 (Study day 1).

Note: Platelet counts conducted locally will be used for efficacy analyses. Platelet counts conducted centrally will be used as a back-up for missed or non-analyzable local lab samples.

Unless otherwise specified,

- Analyses will be performed separately for adult and pediatric populations.
- Analyses will be performed by intervention group (and overall for baseline and demographics characteristics) during the double-blind period.
- Analyses will be performed in the participants who have been exposed to rilzabrutinib during each respective period for OL and LTE. Please refer to [Section 2](#), [Section 3.6](#), [Section 3.6.2](#), [Section 3.6.3](#).
- Cumulative safety analyses across periods will be based on rilzabrutinib safety population. Please refer to [Section 2](#), [Section 3.6](#), [Section 3.6.2](#), [Section 3.6.3](#).
- Limited analyses will be provided during the initial 12 weeks of double-blind treatment period before participants cross over to open-label period to have a full safety profile (see [Table 7](#)).

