### ***Observation period***

The observation period will be divided into 3 segments:

- The **pre-treatment period** is defined as the period up to first double-blind IMP administration.
- **Double-blinded (DB) period**
  - The DB on-treatment period is defined as the period from the first DB IMP administration to the last DB IMP administration + 1 day for participants who did not enter the OL period or to the first OL IMP (the first OL visit is the nominal protocol visit Week 25) for participants who entered the OL period.
  - The DB post-treatment period is defined as the period after the DB on-treatment period for participants who did not enter the OL period.
- **Open-Label (OL) period**
  - The OL on-treatment period is defined as the period from the end of the DB on-treatment period to the last OL IMP administration + 1 day for participants who did not enter the LTE period or to the first OL IMP during the LTE (the first LTE visit is the nominal protocol visit Week 53) for participants who entered the LTE period.
  - The OL post-treatment period is defined as the period after the OL on-treatment period for participants who did not enter the LTE period.
- **Long-term extension (LTE)**
  - The LTE on-treatment period is defined as the period from the end of OL on-treatment period to the last IMP administration + 1 day.

- The LTE post-treatment period is defined as the period after the LTE on-treatment period to the end of study.

Note: Per protocol, the end of study visit occurs 4 weeks post last dose of IMP during the DB, OL or LTE period, whichever later.

Events occurred after the first double-blind IMP administration are considered treatment emergent, including on- and post-treatment events, as defined above. That is, **double-blind treatment-emergent period** includes double-blind on- and post-treatment period. **Open label treatment-emergent period** and **LTE treatment-emergent period** are defined similarly. For rilzabrutinib safety population, the entire treatment-emergent period will start from the 1st administration of rilzabrutinib.

For safety analysis, the 12-week double-blind treatment emergent period is the double-blind treatment emergent period for those discontinued before Week 13 (Day 85) or the period from the first double-blinded IMP administration to the visit date of Week 13 otherwise.

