### **Quantitative analyses**

For all laboratory variables, vital signs, and ECG variables above, descriptive statistics for results and changes from baseline will be provided for each scheduled visit (including the last value on-treatment) during the on-treatment period ([Section 3.1](#)). These analyses will be performed using central measurements only for laboratory variables.

For selected laboratory parameters, mean change (or percent change) from baseline may be plotted over time.

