### **Analyses according to PCSA**

Potentially clinically significant abnormality (PCSA) analyses will be performed based on the PCSA list currently in effect at Sanofi at the time of the database lock ([Section 5.6](#)). For parameters for which no PCSA criteria are defined, similar analyses will be done using the normal range, if applicable. For parameters defined as efficacy endpoints, PCSA summaries will not be provided.

Analyses according to PCSA will be performed based on the worst value during the treatment-emergent period, using all measurements (either local or central, either scheduled, nonscheduled or repeated).

For laboratory variables, vital signs, and ECG variables above, the incidence of participants with at least one PCSA during the treatment-emergent period will be summarized regardless of the baseline level and according to the following baseline status categories:

- Normal/missing
- Abnormal according to PCSA criterion or criteria

For ECG, the incidence of participants with at least one abnormal ECG during the treatment-emergent period will be summarized regardless of the baseline level and according to the following baseline status categories:

- Normal/Not evaluable/Not done
- Abnormal - Not Clinically significant
- Abnormal - Clinically significant

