**Table 9 - Analyses of laboratory variables, vital signs and electrocardiograms**

		DB 24W		OL a	LTE b	DB+OL+LTE c
		Adults	Pediatrics	Adults and Peds Separately		
Laboratory, vital signs, ECG	Descriptive summary d	✓	✓	✓	✓	
	Overtime (by-visit) plot d	✓	✓	✓	✓	
	PCSA (or PCSA-like) shift summary	✓	✓	✓	✓ d	✓ d
DILI	Time to first onset	✓	✓	✓		
	Plot of peak values of ALT versus peak values of total bilirubin	✓	✓	✓		✓
	Return to baseline PCSA status summary	✓	✓	✓		✓

a Cumulative data from 1st dose of rilzabrutinib during OL period. Adult and pediatric populations separately.

b Cumulative data from 1st dose of rilzabrutinib during LTE period. Adult and pediatric populations separately.

c Cumulative data from 1st dose of rilzabrutinib regardless of period. Adult and pediatric populations separately.

d For selected laboratory tests only.

DB = double-blind period; OL = open-label period; LTE = long-term extension; 24W = 24-week double-blind period;

DILI = drug-induced liver injury; ECG = electrocardiograms; PCSA = Potentially Clinically Significant Abnormalities; ALT = alanine aminotransferase.

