eGFR (mL/min/1.73m2) (Estimate of GFR based on an MDRD equation)	<15 (end stage renal disease) ≥15 - <30 (severe decrease in GFR) ≥30 - < 60 (moderate decrease in GFR) ≥60 - <90 (mild decrease in GFR) ≥ 90 (normal GFR)	FDA draft Guidance 2010 Pharmacokinetics in patients with impaired renal function-study design, data analysis, and impact on dosing and labeling
Creatinine	≥150 µmol/L (Adults) ≥30% change from baseline ≥100% change from baseline	Benichou C., 1994.
Uric Acid Hyperuricemia Hypouricemia	>408 µmol/L <120 µmol/L	Harrison- Principles of internal Medicine 17 th Ed., 2008.
Blood Urea Nitrogen	≥17 mmol/L	
Chloride	<80 mmol/L >115 mmol/L	
Sodium	≤129 mmol/L ≥160 mmol/L	
Potassium	<3 mmol/L ≥5.5 mmol/L	FDA Feb 2005.
Total Cholesterol	≥7.74 mmol/L	Threshold for therapeutic intervention.
Triglycerides	≥4.6 mmol/L	Threshold for therapeutic intervention.
Lipasemia	≥3 ULN	
Amylasemia	≥3 ULN	

**CRITERIA for POTENTIALLY CLINICALLY SIGNIFICANT ABNORMALITIES  
for phase 2/3 studies (oncology excepted)**

Parameter	PCSA	Comments
Glucose		
Hypoglycaemia	≤3.9 mmol/L and <LLN	ADA May 2005.
Hyperglycaemia	≥11.1 mmol/L (unfasted); ≥7 mmol/L (fasted)	ADA Jan 2008.
HbA1c	>8%	
Albumin	≤25 g/L	
CRP	>2 ULN or >10 mg/L (if ULN not provided)	FDA Sept 2005.
Hematology		
WBC	<3.0 Giga/L (Non-Black); <2.0 Giga/L (Black) ≥16.0 Giga/L	Increase in WBC: not relevant. To be interpreted only if no differential count available.
Lymphocytes	>4.0 Giga/L	
Neutrophils	<1.5 Giga/L (Non-Black); <1.0 Giga/L (Black)	International Consensus meeting on drug-induced blood cytopenias, 1991. FDA criteria.
Monocytes	>0.7 Giga/L	
Basophils	>0.1 Giga/L	
Eosinophils	>0.5 Giga/L or >ULN (if ULN≥0.5 Giga/L)	Harrison- Principles of internal Medicine 17 th Ed., 2008.
Hemoglobin	≤115 g/L (Male); ≤95 g/L (Female) ≥185 g/L (Male); ≥165 g/L (Female)  Decrease from Baseline ≥20 g/L	Criteria based upon decrease from baseline are more relevant than based on absolute value. Other categories for decrease from baseline can be used (≥30 g/L, ≥40 g/L, ≥50 g/L).
Hematocrit	≤0.37 v/v (Male) ; ≤0.32 v/v (Female) ≥0.55 v/v (Male) ; ≥0.5 v/v (Female)	
RBC	≥6 Tera/L	Unless specifically required for particular drug development, the analysis is redundant with that of Hb. Otherwise, consider FDA criteria.
Platelets	<100 Giga/L ≥700 Giga/L	International Consensus meeting on drug-induced blood cytopenias, 1991.

**CRITERIA for POTENTIALLY CLINICALLY SIGNIFICANT ABNORMALITIES  

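### The SAP never resets the safety baseline at crossover, so placebo-period change enters the open-label and long-term rilzabrutinib laboratory, vital-sign and ECG tables

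*SAP*

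**What the plan says.** SAP 3.1 defines the general baseline: "The baseline value is defined as the last available value before the first dose of double-blind investigational medicinal product (IMP". Participants randomized but never treated take the last value before randomization, and platelet count has its own averaged pre-dose baseline. The other baseline rules deal with different matters: use of unscheduled values (SAP 5.4), a missing ITP-PAQ baseline score (3.3.1.2.4) and missing baseline questionnaires (3.7.3). None sets a new reference value at the start of OL.

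The observation window does move. Under Observation period in SAP 3.1: "For rilzabrutinib safety population, the entire treatment-emergent period will start from the" first rilzabrutinib administration. Table 9 describes its combined-period column as "Cumulative data from 1st dose of rilzabrutinib regardless of period", and its OL column likewise starts at the first OL rilzabrutinib dose.

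Who is included: "Analyses will be performed in the participants who have been exposed to rilzabrutinib during each respective period for OL and LTE". The OL population in Table 3 therefore contains former placebo participants. A split by intervention group is stated only for the double-blind period.

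Three kinds of output use the baseline value:

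- Quantitative summaries: "For all laboratory variables, vital signs, and ECG variables above, descriptive statistics for results and changes from baseline" at each scheduled visit of the on-treatment period. On that row Table 9 carries the footnote "For selected laboratory tests only", so text and table differ on how many variables are covered.
- PCSA incidence, which "will be summarized regardless of the baseline level and according to the following baseline status categories". The LTE and combined-period cells carry the same footnote.
- PCSA criteria that are themselves changes, such as hemoglobin "Decrease from Baseline ≥20 g/L". SAP 5.6.1 also lists creatinine, weight and QTc criteria of this kind, and several vital-sign criteria that pair a threshold with a change.

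Protocol 10.3.1 leaves the handling of open-label data to the SAP.

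**The concern.** For participants randomized to rilzabrutinib, the double-blind baseline is also the last value before rilzabrutinib. For participants randomized to placebo it is not, because a stretch of placebo treatment lies between baseline and first exposure. Followed as written, the SAP gives baseline two meanings within one OL, LTE or combined-period table.

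Take an abnormality that begins on placebo and persists after crossover. It is counted in a rilzabrutinib-period table in the normal/missing baseline row, where it looks like a new abnormality on drug. A hemoglobin fall that was complete before crossover can still satisfy the change criterion in OL.

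Protocol 2.5 gives access to drug for placebo participants and the accrual of long-term rilzabrutinib safety data as purposes of the OL period. The tables also matter early: Step 1 in SAP Table 10, the adult analysis that supports registration, already covers safety by period and cumulatively. What is at stake is accurate attribution in the long-term safety description.

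**Working it through.** The plan states no figure to reproduce. The check is on the text, followed by arithmetic on planned numbers.

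**1. Lag between baseline and first rilzabrutinib dose.** Protocol Table 2 (footnotes o and p) puts OL entry at the Week 13 visit (Study Day 85) for early entrants and at Week 25 (Study Day 169) for completers. 85 − 1 = 84 days and 169 − 1 = 168 days, that is 12 to 24 weeks. Those who leave blinded treatment between Weeks 13 and 24 fall in between.

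**2. Outputs affected, for placebo-origin participants only.**

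| Output | OL | LTE | Combined periods |
|---|---|---|---|
| Change-from-baseline summary | yes | yes | not planned |
| PCSA split by baseline status | yes | selected laboratory tests | selected laboratory tests |
| PCSA criteria defined by change | yes | only if the test is selected | only if the test is selected |
| Absolute-threshold PCSA, regardless of baseline | no | no | no |
| TEAE tables | no | no | no |

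The double-blind tables are also unaffected.

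**3. Placebo-origin share of OL.** Planned arms are 129 and 65 adults, and 20 and 10 children. With entry fractions a (placebo) and b (rilzabrutinib), the adult share is w = 65a / (65a + 129b). The documents give no entry rates, so a and b are assumed:

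- a = b: 65/194 = 33.5%
- a = 0.6, b = 1: 39/168 = 23.2%
- a = 1, b = 0.6: 65/142.4 = 45.6%

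For children with equal entry the share is 10/30 = 33.3%.

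**4. Effect on a pooled mean change.** Let d be the mean placebo-period change, and r_P and r_R the mean changes measured from the last pre-rilzabrutinib value in each origin group. With the study baseline the pooled mean is w(d + r_P) + (1 − w)r_R. With the reset it is w·r_P + (1 − w)r_R. The difference is w·d, which is 0.23 to 0.46 of any placebo-period drift.

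**5. Effect on PCSA tables.** Assume 2% to 10% of placebo-origin entrants carry a given placebo-onset abnormality that persists (not in the documents).

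- Adults who change baseline-status row: 65 × 0.02 = 1.3 to 65 × 0.10 = 6.5 if all cross over; 39 × 0.02 = 0.8 to 39 × 0.10 = 3.9 if 60% do.
- Children, all crossing: 0.2 to 1.0.
- For change-defined criteria the overall OL rate moves too. At 5%: 1.95/168 = 1.2 points, 3.25/194 = 1.7 points, 3.25/142.4 = 2.3 points.

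**6. Hemoglobin illustration.** Assume a normal change with SD s of 8 to 12 g/L, no true change on rilzabrutinib, drift d on placebo, w = 0.335, and one measurement per participant (the SAP uses the worst value, so this is only indicative). Pooled rate of a fall of at least 20 g/L = 0.335·Φ((−20 − d)/s) + 0.665·Φ(−20/s).

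- s = 8, d = −5: 1.4%, against 0.6% after the reset
- s = 12, d = −10: 10.0%, against 4.8%
- d = 0: the two agree

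**The case against.** A single pre-treatment baseline is a defensible convention. Protocol 5.2 protects it: no rescue medication, and no material change in corticosteroid or TPO-RA dose, in the 14 days before Day 1. Crossover values have no such protection. Rescued non-responders may enter OL after 12 weeks, and rescue includes high-dose corticosteroid and IVIg. This stands, and it is why a study-baseline version should be kept beside the reset one. It does not justify leaving placebo-period change unmarked in rilzabrutinib tables.

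The consequence is also limited. SAP 3.6 makes the safety analyses descriptive and untested. Observed values are summarized alongside changes, placebo-period abnormalities appear in the double-blind placebo column, and QTc increases above 60 ms are identified in individual listings. An uncontrolled OL table cannot settle causality under either baseline. All of this stands and keeps the point small.

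Three stronger readings are tempting, and the documents do not support them:

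- A reader might infer that the SAP rules out showing OL and LTE tables by original arm. It does not say so. The by-group statement covers only the double-blind period and the rest is silence; SAP 3.3.2.1 does use the original arm after crossover for stability of response.
- A reader might infer that hemoglobin and creatinine are affected in the LTE and combined-period tables. Those cells cover selected tests, and the selection is not given.
- A reader might count as misplaced a participant who was abnormal before Day 1, normalized on placebo and became abnormal again on drug. Filing that person as abnormal at baseline is arguably right, because the abnormality did pre-exist.

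**Conclusion.** The point holds. It follows from a stated rule that gives a worse result when applied as written: the window restarts at first rilzabrutinib exposure and the reference value does not. The SAP already restarts the clock for placebo participants when it defines initial response for the stability endpoint, so a matching safety rule would be consistent with its own practice.

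The severity is low: something to consider. The share of the OL population affected follows from planned numbers, 33.5% of adults with equal entry and 23.2% to 45.6% under the assumed unequal entry. The number of results misplaced is unknown, because the documents give neither OL-entry rates nor placebo-onset rates. The 1.2 to 2.3 point shift rests on an assumed 5% rate with every such abnormality persisting, and applies only to change-defined criteria in OL. A reader might infer that the trial's adverse event findings or treatment comparison are in doubt; neither uses this reference value after crossover, so neither is.

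**What to change.** Add to SAP 3.1: for participants randomized to placebo, the baseline for OL, LTE and combined-period laboratory, vital-sign and ECG outputs (change from baseline, PCSA baseline status and change-defined PCSA criteria) is the last available value before the first rilzabrutinib dose.

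Show the OL and LTE versions of these tables by original randomized arm. The reset alone would still pool unlike exposures: at nominal Week 29 a former placebo participant has about 4 weeks on drug and a rilzabrutinib-randomized participant up to about 28.

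Keep the study baseline for the double-blind and efficacy analyses and for the liver return-to-baseline summary in SAP 3.6.3.1. A reset there would let an ALT elevation already present at crossover count as back at baseline. Provide a study-baseline version of the OL and LTE tables for reference, because some crossover values follow rescue medication. In the same edit, state whether the text or the Table 9 footnote governs which variables are summarized.

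The cost is small. No new data are needed: Week 13 non-responders, Week 13 to 24 switchers and Week 25 completers all have the Week 25 assessments at OL entry (Protocol Table 1 footnotes b and w; Table 2 footnotes o and p). The price is two labelled baselines and some extra tables. ALT may also carry one baseline status in the shift table and another in the liver summary, which needs a footnote.

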#### *General considerations for efficacy analyses*

The statistical tests will be two-sided tests at a nominal 5% significance level for primary efficacy endpoint and key secondary efficacy endpoints.

Primary and secondary efficacy analyses will be performed in the ITT population, unless otherwise specified. The analyses of primary and key secondary endpoints are to compare the rilzabrutinib treatment group and the placebo treatment group.

The study primary and key secondary efficacy analyses will be based on the adult population at the time when the last adult participant has completed the 24-week blinded treatment period. The results based on the adults at the early analysis will be considered as final and serve as the basis

for registration application submissions. A separate analysis for the pediatric population will be similarly performed after pediatric participants have completed the blinded treatment period which may be at the same or different time when the adults have completed the blinded treatment period. The efficacy analyses on the pediatric population will be descriptive. Final analysis will be performed at the completion of the study. Additional analyses (eg, OL and LTE parts) may be performed before the final analysis. Please refer to [Section 3.8](#) for more details.

The randomization stratification factors will include splenectomy status (yes, no) and severity of thrombocytopenia (platelet counts  $<15,000/\mu\text{L}$ ,  $\geq 15,000/\mu\text{L}$ ).

For platelet count, a scheduled measurement will be used if it is available. Otherwise, an unscheduled measurement will be allocated to a scheduled visit if it is within the analysis window of the scheduled visit (see details in [Section 5.4](#)).

Rescue medications are recorded in eCRF by the investigator. Per protocol, rescue medications include IVIg, high-dose CSs, platelet infusion, and anti-D immunoglobulin infusion intended to increase platelet counts or prevent bleeding when platelet counts are less than  $20,000/\mu\text{L}$ , or for bleeding or wet purpura. Other rescue medications are not permitted.

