6.6.2. Particular Permissible Medications

The following medications are permitted for use during the study:

- ITP medications, an oral CS and/or a TPO-RA (authorized for the treatment of ITP)

Note:

- These medications must be maintained at stable doses from 14 days before Study Day 1 and until the last dose of study medication. Adjustments in the doses of concomitant ITP medications will be permitted for associated safety concerns only.
- Administration of corticosteroids and TPO-RAs should follow corresponding updated package inserts/SmPCs of the marketing authorization.
- Tapering is allowed during LTE period only due to achieving durable platelet response, and would follow the following guidelines with 2 weekly platelet counts between tapers:
 - 10 mg/day every one to two weeks from an initial dose >40 mg of prednisone or equivalent per day
 - 5 mg/day every one to two weeks at prednisone doses ≤ 40 to >20 mg or equivalent per day
 - 2.5 mg/day every one to two weeks at prednisone doses ≤ 20 to >10 mg or equivalent per day
 - 1 mg/day every one to two weeks at prednisone doses ≤ 10 to >5 mg or equivalent per day
 - 0.5 mg/day every one to two weeks at prednisone doses ≤ 5 mg or equivalent per day down to zero. This can be achieved by alternating daily doses (eg, 5 mg on day one and 4 mg on day two)
 - Dose of corticosteroid can be up titrated if platelet counts fall below $50,000/\mu L$ on two consecutive measurements
- IVIg or high- dose CS, platelet infusion, or anti-D immunoglobulin infusion as rescue medications

- Clinically relevant drugs that are substrates of CYP3A, including those considered to be sensitive CYP3A substrates. Appropriate caution should be used when co-administering sensitive CYP3A substrates with rilzabrutinib, including an assessment of medical risk-benefit for each medication. Consideration should also be given to avoidance of high doses, dose reduction, or replacement of sensitive CYP3A substrate drugs
- H₂ receptor blocking drugs (ranitidine or famotidine) and antacids are permitted provided they can be given 2 hours or more after administration of rilzabrutinib or placebo

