10. STATISTICAL METHODS

A detailed Statistical Analysis Plan (SAP) will be developed and finalized before the study database is locked which will supersede the statistical analysis methods described in the protocol; however, any major modification of the outcome measures and/or its analysis will also be reflected in the clinical study report (CSR).

Descriptive summaries of variables by treatment will be provided where appropriate. Generally, continuous variables will be summarized using the following descriptive statistics: mean, standard deviation, number of observations, median, minimum, and maximum. Summaries will also be presented for the change from baseline, when appropriate. For categorical variables, the counts and proportions of each value will be tabulated by treatment. For time to event variables, point estimates (25th, 50th, and 75th percentiles) along with 95% confidence intervals will be tabulated by treatment using Kaplan-Meier methods. Survival estimates will also be shown graphically for each treatment.

All statistical tests will be two-sided unless otherwise noted.

The pediatric participants will not be tested, and descriptive statistics will be done on these participants. Additional statistical analyses on these pediatric participants may be provided for specific regulatory requests.

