10.3.9. Primary Efficacy Analysis

The primary analysis will compare the proportion of participants in the adult ITT population who achieve durable platelet response defined as platelet counts at or above 50,000/ μ L for \geq two-thirds of at least 8 non-missing weekly scheduled platelet measurements during the last 12 weeks of the 24-week blinded treatment period in the absence of rescue medication (provided that at least 2 non-missing weekly scheduled platelet measurements are at or above 50,000/ μ L during the last 6 weeks of the 24-week blinded treatment period) between rilzabrutinib and placebo with a Cochran-Mantel-Haenszel test using the two stratification factors at a 2-sided alpha level of 0.05 (see [Appendix 10.7](#) for a description of the primary efficacy analysis in the EU [EEA countries] and UK). Participants who do not respond in the first 12 weeks and enter the open label period will be treated as non-responders in the primary analysis. Participants who discontinue the study due to a rilzabrutinib-related AE lack of efficacy or receive rescue medication (including an increase in allowed concomitant ITP medications dose) will be considered as non-responders. Sensitivity analyses will be conducted on the primary analysis.

The primary endpoint will be analyzed for adult and pediatric participants separately.

Platelet counts conducted locally will be used for the primary endpoint analysis. Platelet counts conducted centrally at Clinic Visits will be used as a back-up for missed or non-analyzable local lab samples.

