#### 3.2.1 Definition of endpoint(s)

Please refer to [Section 1.2.2.1](#) for primary efficacy endpoint.

To qualify for a durable responder (Definition 1, [Section 1.2.2.1](#)), a participant must have met ALL of the following criteria:

- At least 8 non-missing weekly platelet measurements during the last 12 weeks of the 24-week treatment period, and
- Platelet counts  $\geq 50,000/\mu\text{L}$  for  $\geq$ two-thirds of the 8 non-missing weekly assessments above, and
- At least 2 platelet counts  $\geq 50,000/\mu\text{L}$  occurred during the last 6 weeks of the 24-week treatment period, and
- Not rescued after 8 weeks of treatment and before Week 25 (or last IMP intake, whichever earlier). A participant who is rescued during this period will be considered as a non-responder, and
- Not discontinued before Week 25 due to related TEAE (per investigator's assessment) or lack of response. A participant who discontinues before Week 25 and the reason for discontinuation is treatment related adverse event (AE) or lack of response will be considered as a non-responder.

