### 3.2.2 Main analytical approach

The main analysis of the primary endpoint is to compare the responder rate of the rilzabrutinib treatment group with the placebo treatment group via the primary estimand as defined in [Table 2](#).

To reject the null hypothesis of no treatment difference, the two-sided p-value based on a Cochran-Mantel-Haenszel (CMH) test adjusted by randomization stratification factors ([Section 3.1](#)) must be  $<0.05$  in the adult ITT population. The Mantel-Haenszel estimate of common risk difference in response rates and its associated 95% confidence interval based on Mantel-Haenszel stratum weights (1) and the Sato variance estimator (2) will be reported. The observed response rate for each treatment group will be presented along with its associated 95% asymptotic confidence interval (CI).

For pediatric participants, the observed response rate will be calculated along with its associated (90% and 95%, respectively) CI in each treatment group using the Clopper-Pearson exact method. The difference in response rate and its associated 95% exact CI will be presented.

For Pharmaceuticals and Medical Devices Agency (PMDA) in Japan, the consistency of efficacy in pediatric population will be assessed with Method 2: the difference in response rate in the pediatric population is in the same direction as that in the adult population (ie, the response rate in rilzabrutinib group is numerically higher than that in the placebo group in the pediatric population) given that the treatment effect in adults is significant (ie,  $p\text{ value} < 0.05$ ).

Graphical presentations of the results will be provided as needed. SAS® sample code could be found in [Section 5.7](#).

**Intercurrent events** will be handled with the primary estimand specified in [Table 2](#). Specifically,

1. Rescue medication: participants will be considered as non-responders if taking rescue medication after 8 weeks of double-blind treatment and before Week 25 (or last IMP intake, whichever earlier) (composite strategy).

2. Discontinuation of study intervention before Week 25 due to lack of response or related AE (per investigator's assessment in eCRF): participants will be considered as non-responders (composite strategy).

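### The protocol scores an increase in concomitant ITP medication dose as non-response on the primary endpoint; the SAP has no such rule and does not declare the difference

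*SAP*

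**What the plan says.** Protocol 10.3.9 (Primary Efficacy Analysis) says that participants who "receive rescue medication (including an increase in allowed concomitant ITP medications dose) will be considered as non-responders". Appendix 10.7 repeats the same parenthesis for the EU/EEA and UK primary analysis, so both versions of the endpoint carry it.

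The SAP's general considerations for efficacy analyses state the data source, "Rescue medications are recorded in eCRF by the investigator", then the content: "Per protocol, rescue medications include IVIg, high-dose CSs, platelet infusion, and anti-D immunoglobulin infusion intended to increase platelet counts", and then "Other rescue medications are not permitted". The responder criteria in SAP 3.2.1 require, for both Definition 1 and Definition 2, "Not rescued after 8 weeks of treatment and before Week 25 (or last IMP intake, whichever earlier". The first intercurrent event in SAP 3.2.2 and Table 2 is worded to match: "participants will be considered as non-responders if taking rescue medication after 8 weeks of double-blind treatment and before Week 25". None of these places mentions an increase in corticosteroid (CS) or TPO-RA dose, and neither does Table 5.

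On precedence, Protocol 10 describes a SAP "which will supersede the statistical analysis methods described in the protocol", and the synopsis makes the SAP the final authority while asking it to draw attention to changes of substance. On dosing, Protocol 6.6.2 requires stable concomitant ITP doses and says "Adjustments in the doses of concomitant ITP medications will be permitted for associated safety concerns only".

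**The concern.** CS and TPO-RAs are given in ITP to raise platelets, and the endpoint is a platelet count of at least 50,000/µL sustained over the last 12 blinded weeks. If a background dose is raised and the count then holds, the response cannot be credited to the randomised treatment. The protocol's primary analysis section provides for this case and scores it as non-response. The SAP, which governs, leaves it unaddressed.

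The confirmatory endpoint therefore has two responder rules that can classify the same participant differently. The SAP's sensitivity analyses would not expose the difference: those in SAP 3.2.3 and Table 4 vary the handling of missing data or the analysis population, never the treatment of a dose increase. If the question is first met after unblinding, the choice of rule will be made with the results in view.

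**Working it through.** **Step 1. Place the texts side by side.**

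| Place | Dose increase scored as non-response? |
|---|---|
| Protocol 10.3.9 | Yes |
| Protocol Appendix 10.7 (EU/EEA and UK) | Yes |
| Protocol synopsis, primary efficacy analysis | Not mentioned |
| Protocol rescue lists (synopsis, Sections 4 and 6.6.1) | Not mentioned; four agents only |
| SAP 3.1, rescue description | Not mentioned; the same four agents |
| SAP Table 2, primary estimand | Not mentioned |
| SAP 3.2.1, Definitions 1 and 2 | Not mentioned |
| SAP 3.2.2, intercurrent events 1 to 3 | Not mentioned |
| SAP Table 5, tipping-point status | Not mentioned |
| SAP Table 1 and Section 3.9, declared changes | Not mentioned |

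Take a participant whose TPO-RA dose is raised in Week 15, who stays on blinded treatment, and whose later counts meet the threshold. Protocol 10.3.9 gives non-responder. SAP 3.2.1 gives responder unless the investigator enters the increase as rescue, and a TPO-RA is not among the listed rescue agents.

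**Step 2. Reproduce the plan's power.** Inputs from SAP 4 and Protocol 10.1: n = 129 and 65, response 25% versus 5%, two-sided Fisher's exact test at 0.05. Power is the sum of Bin(x; 129, p1) × Bin(y; 65, p0) over all tables (x, y) with Fisher p ≤ 0.05. The result is 96.4%; a normal approximation gives 96.5%. The stated 95% reproduces, so the sample size is not in question.

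**Step 3. Show what misclassification could do.** No up-dosing rate is given. The shifts below are assumptions: the share of an arm scored as responder only because a dose increase is not counted.

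| Assumed shift | Response rates | Power |
|---|---|---|
| None | 25% v 5% | 96.4% |
| Placebo +2 points | 25% v 7% | 88.8% |
| Placebo +3 points | 25% v 8% | 83.1% |
| Both arms +2 points | 27% v 7% | 93.6% |
| Both arms +5 points | 30% v 10% | 89.7% |

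With no true effect (5% in both arms), the probability of a significant result favouring rilzabrutinib is:

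| Assumed shift | Response rates | Probability |
|---|---|---|
| None | 5% v 5% | 0.9% |
| Rilzabrutinib +2 points | 7% v 5% | 3.8% |
| Rilzabrutinib +5 points | 10% v 5% | 15.1% |

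**Step 4. Translate into participants.** One reclassified participant moves the rilzabrutinib rate by 1/129 = 0.8 points and the placebo rate by 1/65 = 1.5 points. Three points in placebo is 0.03 × 65 = about 2 participants; two points in rilzabrutinib is 0.02 × 129 = 2.6, about 3 participants.

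**The case against.** The strongest reply is that the SAP did follow the protocol. Its four agents are the ones named in the protocol's own rescue lists, the endpoint in Protocol 3.2.1 speaks only of absence of rescue therapy, and the synopsis version of the primary analysis lacks the parenthesis. This stands in part. The protocol is not consistent with itself, and a reader might infer that the SAP struck out a settled rule or fails to test the protocol's primary endpoint. The documents do not support that reading. They show that the SAP matches the rescue lists but not the section that defines the primary analysis.

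Second, the event should be uncommon. Protocol 6.6.2 restricts dose adjustments to safety concerns, so an increase made for efficacy would be a deviation. The participant must also have met the Week 12 response rule to stay blinded, and then have reached 50,000/µL on at least two-thirds of the late measurements. All of this limits the number. It does not remove the case: the analysis is intention-to-treat, so such participants stay in and need a classification.

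Third, the increase may already be captured. A large CS increase could be entered as high-dose rescue, and the eCRF instructions are not in the documents. That covers part of the CS route. The SAP gives no stated route for a TPO-RA increase or a modest CS increase.

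Finally, the SAP says it is based on amended protocol 03, whose full text is not supplied. The amendment history shows no later insertion of the parenthesis, but its presence in that version cannot be confirmed.

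**Conclusion.** The inconsistency is real and bears on who counts as a primary-endpoint responder. It should be resolved before unblinding. It rests on the wording alone and not on any assumed rate.

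Its numerical effect is unknown. A reader might infer that the omission favours rilzabrutinib, or that it costs substantial power. Neither follows. Increases concentrated in placebo dilute the contrast (83.1% power at 25% versus 8%), similar increases in both arms matter little (93.6% at 27% versus 7%), and increases confined to the active arm raise the false-positive chance (0.9% to 3.8% for 2 points). Every one of these shifts is assumed, and each counts only participants who become responders solely because the increase is ignored.

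A reader might also take the key secondary platelet endpoints to be wrong in the same way. The protocol states the dose-increase rule only for the primary analysis, so there is no contradiction there.

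**What to change.** Before unblinding, carry the scoring rule of Protocol 10.3.9 and Appendix 10.7 into SAP 3.1, 3.2.1 (both definitions), 3.2.2, Table 2 and Table 5, derived from the concomitant ITP medication dosing records and not only from investigator-entered rescue. Two details must be specified:

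- **Time window.** The protocol sets none for dose increases. Borrowing the SAP's after-8-weeks limit for rescue would miss a dose raised in, say, Week 6 and kept raised through the last 12 weeks. The window should capture an earlier increase that is maintained into that period.
- **What counts as an increase.** Neither document defines it for scoring. The only nearby figure, the more-than-10% variation in exclusion criterion 6, was written for eligibility.

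Record the reconciliation in SAP 3.9 and align the protocol synopsis and rescue lists with 10.3.9. If the sponsor instead intends to drop the rule, that should be declared and justified in 3.9; Protocol 10 also requires major modifications to appear in the study report. Extending the rule to the key secondary endpoints is optional.

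The cost is SAP wording and one derivation from records already collected at clinic visits. A few responders may be reclassified. Sample size, alpha and the test are unchanged.
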